## **5.8 Drug Dispensing Requirements**

In investigational studies, eltrombopag will be dispensed through a qualified healthcare professional (including but not limited to, nurses, pharmacists and physicians). These healthcare professionals will be trained in requirements specific to counseling of subjects. Once trained these healthcare staff will counsel subjects prior to medication being dispensed to ensure that the subject has complied with all requirements including use of birth control and pregnancy testing and that the subject understands the risks associated with eltrombopag. In all females of child bearing age, negative result of required pregnancy testing will be verified and documented.

## **5.9 Standard of Care Therapies**

Participants should receive all supportive care therapies (blood product transfusions, antibiotics, antiemetics, growth factors, etc.) that are required for treatment of the symptoms of disease or for infections or other adverse events.

## **5.10 Concomitant Medications and Non-drug Therapies**

### **5.10.1 Permitted Medications and Non-Drug Therapies**

A reasonable effort will be made to document any medications the subject received within the 30 days prior to the first day in the study. If any medication is required at any time within 7 days before first day in the study through the completion of the short-term follow-up visit, subjects should consult the investigator.

### **5.10.2. Use of Growth Factors**

Subjects will not be allowed to receive granulocyte colony stimulating factor (G-CSF)/pegylated G-CSF, or other growth factors (e.g., epoetin alfa) during this study. Use of these drugs is not considered standard institutional practice at Cleveland Clinic during IC for AML.

### **5.10.3. Food, Antacids, Cations and Vitamin/Mineral Supplements**

Eltrombopag should be taken on an empty stomach (1 hour before or 2 hours after a meal). Allow at least a 4 hour interval between eltrombopag and other medications or products containing polyvalent cations (e.g. calcium, magnesium, aluminum, zinc selenium or iron) such as antacids, dairy products, and mineral supplements to avoid significant reduction in eltrombopag absorption due to chelation.

Administration of eltrombopag with a polyvalent cation-containing antacid decreased plasma eltrombopag exposure by 70%, and a similar reduction was observed when eltrombopag was administered with a high-calcium meal. Therefore, every effort must be made to educate subjects on how to take investigational product with medications or foods containing these polyvalent cations. Details of these and all concomitant medications should be recorded in the CRF.

Subjects requiring routine (e.g. daily) acid suppression should be encouraged to take H2 antagonists like ranitidine, famotidine or nizatidine, or proton pump inhibitors like omeprazole, esomeprazole or lansoprazole. Subjects requiring occasional acid suppression may take liquid or chewable antacids (calcium carbonate, aluminum hydroxide or magnesium hydroxide), provided investigational product is taken at least 4 hours before and 4 hours after consumption of cation-containing antacids.

Mineral supplements (such as calcium, magnesium, aluminum, zinc, selenium or iron) are permitted during the study but investigational product must be taken at least 4 hours before and 4 hours after consumption of these supplements. Similarly, eltrombopag must be taken at least 4 hours before and 4 hours after consumption of dairy products (such as milk, yogurt, and cheese).

### **5.10.4. HMG-CoA Reductase Inhibitors (statins)**

Subjects will be permitted to use HMG-CoA reductase (3-hydroxy-3-methyl-glutaryl-CoA) inhibitors during the study, but these drugs should be used with caution and a 50% dose reduction of the HMG-CoA reductase inhibitor is recommended, with close monitoring for safety, such as liver chemistry and signs and symptoms of myolysis, and efficacy, such as cholesterol and triglycerides (refer to individual product information for monitoring recommendations).

Preclinical data showed that eltrombopag is an inhibitor of the transporters OATP1B1 and BCRP. Therefore, a clinical drug interaction study to evaluate the impact of eltrombopag on the PK of rosuvastatin, an OATP1B1 and BCRP substrate, was conducted in healthy subjects. Co-administration of eltrombopag 75 mg once daily for 5 days with a single 10 mg dose of rosuvastatin administered on Day 5 increased plasma rosuvastatin Cmax 2.03-fold and AUC (0-∞) 55%. Concomitant administration of eltrombopag and other OATP1B1 or BCRP substrates should be used with caution.

#### **5.10.6. Blood product transfusions**

Transfusion of blood products will be allowed as per the Cleveland Clinic institutional guidelines. For details please refer to section 4.1.

### **6.0. SAFETY DATA AND ASSESSMENT**

#### **6.1. Common Side Effects and Toxicities (Reference: Eltrombopag Investigator Brochure)**

A detailed description of safety profile of eltrombopag in clinical pharmacology studies as well as in clinical trials involving patients with chronic liver disease, ITP and Hematology/Oncology related thrombocytopenia studies is available in the Clinical Investigator's Brochure provided by Novartis. The drug related toxicity will be scored based on the National Cancer Institute Common Toxicity Criteria Scale Version 4, which can be obtained from the CTEP website (<http://ctep.cancer.gov/reporting/ctc.html>). The effectiveness and safety of eltrombopag have not been established for use in other thrombocytopenic conditions including chemotherapy-induced thrombocytopenia, myelodysplastic syndromes (MDS) and AML.

#### **6.2 Hepatic monitoring**

Eltrombopag administration can cause hepatobiliary laboratory abnormalities. In clinical studies in chronic ITP with eltrombopag, increases in serum alanine aminotransferase (ALT), aspartate aminotransferase (AST) and indirect bilirubin were observed. These findings were mostly mild (Grade 1-2), reversible and not accompanied by clinically significant symptoms that would indicate impaired liver function. In two placebo controlled studies in chronic ITP, adverse events of ALT increase were reported in 5.7 % and 4.0 % of eltrombopag and placebo treated patients respectively. In 2 controlled clinical studies in thrombocytopenic patients with HCV, ALT or AST  $\geq 3$  x ULN were reported in 34 % and 38 % of the eltrombopag and placebo groups, respectively. Eltrombopag administration in combination with peginterferon/ribavirin therapy is associated with indirect hyperbilirubinaemia. Overall, total bilirubin  $\geq 1.5$  x ULN was reported in 76 % and 50 % of the eltrombopag and placebo groups, respectively. Serum ALT, AST, and total bilirubin should be measured prior to initiation of eltrombopag. If total bilirubin is elevated, fractionation should be performed. If the abnormalities are confirmed, serum hepatic function tests will be monitored daily inpatient as part of standardized care and once weekly as outpatient until the abnormalities are resolved, stabilized or returned to baseline levels.

#### **6.3 Thrombotic/Thromboembolic Complications**

Platelet counts above the normal range present a theoretical risk for thrombotic/thromboembolic complications. In eltrombopag clinical trials in ITP thromboembolic events were observed at low and normal platelet counts. Use caution when administering eltrombopag to patients with known risk factors for thromboembolism (e.g., Factor V Leiden, ATIII deficiency, antiphospholipid syndrome). Platelet counts should be closely monitored and consideration given to reducing the dose or discontinuing eltrombopag treatment if the platelet count exceeds the study target levels. In ITP studies, 21 thromboembolic/thrombotic events were observed in 17 out of 446 subjects (3.8 %). The TEE events included: embolism including pulmonary embolism, deep vein thrombosis, transient ischemic attack, myocardial infarction, ischemic stroke, and suspected PRIND (prolonged reversible ischemic neurologic deficiency). Eltrombopag should not be used in patients with hepatic impairment (Child-Pugh score  $\geq 5$ ) unless the expected benefit outweighs the identified risk of portal venous thrombosis. In 2 controlled studies in thrombocytopenic patients with HCV receiving interferon based therapy, 31 out of 955 subjects (3 %) treated with eltrombopag experienced a TEE (3 %) and 5 out of 484 subjects (1 %) in the placebo group experienced TEEs. Portal vein thrombosis was the most common TEE in both treatment groups (1 % in patients treated with eltrombopag versus < 1 % for placebo). No specific temporal relationship between start of treatment and event of TEE were observed. The majority of TEEs resolved and did not lead to the discontinuation of antiviral therapy. In a controlled study in thrombocytopenic patients with chronic liver disease (n = 288, safety population) undergoing elective invasive procedures, the risk of portal vein thrombosis was increased in patients treated with 75 mg eltrombopag once daily for 14 days. Six of 143 (4 %) adult patients with chronic liver disease receiving eltrombopag experienced thromboembolic events (all of the portal venous system) and two of 145 (1 %) subjects in the placebo group experienced thromboembolic events (one in the portal venous system and one myocardial infarction). Five eltrombopag treated subjects with a TEE experienced the event within 14 days of completing eltrombopag dosing and at a platelet count above 200,000/ $\mu$ l.

#### 6.4 Bleeding Following Discontinuation of eltrombopag

Following discontinuation of eltrombopag, platelet counts return to baseline levels within 2 weeks in the majority of patients, which increases the bleeding risk and in some cases may lead to bleeding. Assessment of bleeding will be performed throughout the study from screening until the last dose of study drug or patient withdrawal from the study. Bleeding will be assessed by the WHO Bleeding Scale (Appendix V: WHO Bleeding Scale). Platelet counts will be monitored as part of daily CBC measurements during the period of hospitalization and thereafter once weekly as outpatient following discharge for 4 weeks following discontinuation of eltrombopag.

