## **4.0 STUDY DESIGN**

### **4.1 Overall Design**

This is a single institution, single arm, non-randomized phase II clinical trial with a sample size of 31 patients. The primary goal of this trial is to determine if eltrombopag can accelerate platelet count recovery in older AML patients (age  $\geq$ 60 years) who have no morphological evidence of leukemia in the bone marrow following remission IC. The standard remission IC for AML in patients  $\geq$ 60 years will consist of an anthracycline (daunorubicin or idarubicin) for 3 days and cytarabine as continuous intravenous infusion for 7 days. The patients in the study will receive supportive blood transfusions as part of standard of care at the Cleveland Clinic. Use of erythropoiesis stimulating agents (ESA) or granulocyte colony stimulating factors (G-CSF) during or following remission IC is not permitted. The study schema is shown below.

In those patients who have no morphologic evidence of disease on day 14 (range, 14-17) bone marrow evaluation, eltrombopag will be administered within 5 business days from the date of day 14 (range, 14-17) bone marrow biopsy. There will be a gap of at least one week (range, 7-9 days) between the last day of remission IC and initiation of eltrombopag, which will allow sufficient time for complete washout of the chemotherapeutic agents. Dose modification will be determined based on platelet counts and presence of adverse event(s).

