### **8.4 Long-term Follow-up**

All participants, regardless of reason for discontinuation, will be followed for survival and for AML transformation (an increase of blasts to a level  $\geq 20\%$  in peripheral blood or bone marrow) for five years from study registration as part of standard of care for CCF leukemia patients.

The following study calendar will be used:

	Pre- induction	Week 1	Week 2	Week 3	Week 4	Week 5	Week 6
						Inpatient/Outpatient	
Induction chemotherapy (IC)							
Study Medicationa							
Informed Consent	X						
Demographicsb	X						
Disease Characteristicsc	X						
Transfusion Historyd	X	X	X	X	X	X	X
Review of concurrent medications	X	X	X	X	X	X	X
Physical Examinatione	X	X	X	X	X	X	X
CSBEf	X	X	X	X	X	X	X
Performance statusg	X						
Hematologyh	X	X	X	X	X	X	X
Serum Biochemistryi	X	X	X	X	X	X	X
Chest x-ray	X						
Peripheral Blood Smearj	X					X	
Bone marrow biopsyk	X		D14 - 17			X	
Ophthalmology examl	X						
12 lead ECG	X			X m			
Adverse event monitoringn				X	X	X	X

Pre-induction assessment refers to evaluation at the time of diagnosis of AML prior to start of remission induction chemotherapy. Weeks as enumerated in the table refer to the time from the start date (day 1) of remission induction chemotherapy.

Week 1 is the week when the patient receives the standard 7+ 3 (cytarabine and anthracycline) remission induction chemotherapy

a. **Study Medication:** Eltrombopag dose as assigned. The drug will be started within 5 business days from the date of day 14 bone marrow biopsy if the day 14 bone marrow biopsy (range, 14-17) shows no morphological evidence of leukemia and will be continued for a total of 4 weeks unless discontinued earlier for reasons stated in the protocol.

b. **Demographics:** Date of birth, race, ethnicity, and gender.

c. **Disease Characteristics:** Date of AML diagnosis, AML category as classified by WHO, primary vs. secondary AML, type of secondary AML (antecedent hematologic disorder, therapy-related including prior radiation therapy and or cytotoxic chemotherapy for any condition).

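### WHO bleeding assessment ends at the last dose (6.4) and the CSBE calendar row at induction week 6, so bleeding after discontinuation has no single defined window and may be understated

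*Combined protocol and SAP*

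**What the plan says.** Section 6.4 is the section on bleeding after the drug is stopped. It says that "platelet counts return to baseline levels within 2 weeks in the majority of patients, which increases the bleeding risk". It then fixes the period of clinical observation, which runs "from screening until the last dose of study drug or patient withdrawal from the study". Platelet counts in the same section go further, daily in hospital and then "once weekly as outpatient following discharge for 4 weeks following discontinuation of eltrombopag".

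The study calendar (under Section 8.4) marks CSBE at pre-induction and in weeks 1 to 6. Its clock is not tied to the drug: "Weeks as enumerated in the table refer to the time from the start date (day 1) of remission induction chemotherapy". Note a says of the start, "The drug will be started within 5 business days from the date of day 14 bone marrow biopsy", and of the duration that treatment "will be continued for a total of 4 weeks unless discontinued earlier for reasons stated in the protocol". Section 4.1 gives a second start rule: "There will be a gap of at least one week (range, 7-9 days) between the last day of remission IC and initiation of eltrombopag".

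Other sections that bear on the window:

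- Section 8.3 (short-term follow-up) lists AE monitoring, blood counts, chemistry, examination and transfusions. It has no WHO or CSBE item and gives no length for the period.
- Section 10.2, item 1, defines CSBE as bleeding that needs intervention, but does not say when counting stops. Section 2.2 makes the CSBE rate a secondary objective and refers to Appendix I (the WHO scale).
- Section 7.8 describes follow-up of up to 4 weeks after stopping, cut short by post-remission therapy, for subjects who reached 100,000/µL. Section 8.2, item 9, repeats this and adds AE collection over the same period.
- Section 11.7 collects AEs and SAEs through short-term follow-up. The reporting text after it requires possibly related SAEs to be reported at any time after the drug is stopped.

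**The concern.** The section that names the hazard follows the laboratory marker through it but stops observing the clinical outcome on the day it begins. The calendar does not repair this, because it counts from induction rather than from the last dose.

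CSBE is a secondary endpoint and part of the safety assessment. With two conflicting ends to observation and none in the endpoint definition, the same patient can give different results depending on the section followed. The period for which 6.4 expects added risk may contribute few or no events by default. The primary endpoint (platelets by day 24) and the two-stage decision rule are not affected.

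**Working it through.** The plan states no figure on this point, so there is nothing to reproduce. The check is a timeline in days from day 1 of induction.

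**Inputs**

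- Calendar end: week 6, day 6 × 7 = 42.
- Start, rule A (calendar note a): within 5 business days of a marrow taken on day 14-17. Taking 5 business days as 7 calendar days without holidays, the start is day 14 to 17 + 7 = 24.
- Start, rule B (Section 4.1): 7-9 days after the last induction day, taken as day 7. The start is day 14-16, or day 17 at the latest if only the full days in between are counted.
- Full course: 28 daily doses.
- Risk window: 14 days after the last dose. This is read from 6.4, which gives the time for counts to fall back but no formal end of risk.

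**Formulas**

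- Last dose = start + 27.
- Calendar days after last dose = max(0, 42 − last dose), capped at 14.
- Dosing days beyond the calendar = max(0, last dose − 42).

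**Full course**

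| Start rule | Start day | Last dose | Of 14 risk days, covered by calendar | Dosing days beyond calendar |
|---|---|---|---|---|
| A, earliest | 14 | 14 + 27 = 41 | 42 − 41 = 1 | 0 |
| A, latest | 24 | 24 + 27 = 51 | 0 | 51 − 42 = 9 |
| B, earliest | 14 | 41 | 1 | 0 |
| B, latest | 17 | 17 + 27 = 44 | 0 | 44 − 42 = 2 |

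Under either rule the calendar covers at most 1 of the 14 days, and only for a start on day 14. Under 6.4 it is 0 of 14 for everyone.

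**Early stop**

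- Last dose day 28: 42 − 28 = 14, so all 14 days are in the calendar.
- Last dose day 34: 42 − 34 = 8 days.
- Last dose day 38: 42 − 38 = 4 days.
- Under 6.4: 0 days in each case.

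**What the conflict does.** A patient stops on day 28 and bleeds on day 35: the event is inside the calendar window and outside the 6.4 window. A patient under rule A has a last dose on day 51 and bleeds on day 47: the event is inside 6.4 and outside the calendar.

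**What full coverage would need.** After a full course, 14 days run to day 55-65 under rule A (41 + 14 to 51 + 14) or day 55-58 under rule B. Four weeks run to day 69-79 or day 69-72. The calendar ends on day 42.

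**The case against.** The best counter-argument is that the protocol does observe patients after the last dose. AEs are collected for up to 4 weeks (8.2), AEs and SAEs through short-term follow-up (11.7), and possibly related SAEs without time limit. Since CSBE is bleeding that needs intervention, the transfusion records in 8.3 hold much of the raw material. This stands, and it rules out saying that bleeding after discontinuation goes unrecorded. What is missing is assessment against the WHO scale and the CSBE definition.

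The substitute is partial for two reasons. Section 11.1 removes expected signs of the disease from the AE definition unless they are worse than expected, which could filter some bleeding. Section 7.8 frames the 4-week follow-up around subjects who reached 100,000/µL, so patients who never reach it have no clearly defined window.

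A reader might infer more than this. Four stronger readings are not supported:

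- **Section 11.5 excludes bleeding.** Its list covers progression, cytopenias and infections, not bleeding, and it applies only to events not attributed to study drug.
- **The period after stopping carries the highest risk.** Section 6.4 says that risk increases and does not rank periods. Section 7.3 stops the drug once untransfused platelets reach 100,000/µL, so some patients stop because counts have recovered.
- **The CSBE rate is biased low.** With no end of window in 10.2, the quantity is undefined rather than demonstrably biased. An on-treatment rate would be a legitimate but different quantity.
- **The calendar ends before the last dose for most full-course patients, by up to 9 days.** Nine days is the extreme under rule A. Under rule B it is at most 2, and no distribution of start days is given.

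**Conclusion.** The point holds as a conflict between sections and a gap in protocol-specified bleeding assessment. Section 6.4 covers none of the two weeks it warns about. The calendar covers 0-1 of those 14 days after a full course, and part or all of them for patients who stop early. Beyond that, bleeding reaches the record only as a general AE or SAE or through a transfusion entry, so CSBE after discontinuation may be understated. By how much cannot be said from the documents.

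This rests on 5 business days being 7 calendar days, induction ending on day 7, 28 uninterrupted daily doses, and a 14-day risk window. The 0-1 day result for a full course is the same under both start rules. The endpoint is secondary and descriptive in a single-arm trial of 31 patients, so this is a worthwhile, inexpensive correction rather than a threat to the main conclusion.

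**What to change.** - In 10.2, state one data-collection window for WHO and CSBE bleeding in all treated patients, whether or not they reached 100,000/µL. Run it to 4 weeks after the last dose, or to the start of post-remission therapy if earlier. Sections 7.8 and 8.2 already use this window.
- Bring 6.4, 7.8, 8.2, 8.3 and the calendar into line. Add a bleeding item to 8.3, and calendar columns counted from the last dose.
- Report CSBE on drug and after drug separately, each with its days of observation.
- Reconcile the two start rules (4.1 and calendar note a), since they give different last-dose days.
- Correct the reference in 6.4 to Appendix V; the WHO scale is Appendix I.

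The cost is wording and about one added CRF item at follow-up contacts. It is not quite free. Calendar note h leaves laboratory checks to the physician's discretion once platelets reach 100,000/µL, whereas 6.4 has weekly outpatient counts for 4 weeks after stopping. Those passages must be reconciled, and until they are, some of the contacts on which the bleeding item would be collected are not guaranteed.

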#### 6.5 Bone Marrow Reticulin Formation and Risk of Bone Marrow Fibrosis

Thrombopoietin (TPO) receptor agonists, including eltrombopag, may increase the risk for development or progression of reticulin fibrosis within the bone marrow. Baseline information on bone marrow reticulin fibrosis is routinely obtained as part of bone marrow evaluation at the time of AML diagnosis at Cleveland Clinic. Prior to initiation of study medication, the peripheral blood smear will be examined to establish a baseline level of cellular morphologic abnormalities.

A follow up peripheral blood and bone marrow smear for any new or worsening morphological abnormalities (e.g., teardrop and nucleated red blood cells, immature white blood cells) will be performed at 6 week time point (from IC) when the remission status is routinely assessed (i.e. day ~30-45 bone marrow). If any new abnormalities are detected, additional bone marrow biopsies will be performed at periodic intervals based on clinical judgment.

## 6.6 Malignancies and progression of malignancies

There is a theoretical concern that TPO-R agonists may stimulate the progression of existing hematological malignancies such as MDS. Across the clinical trials in ITP (n = 493) and HCV (n = 1439) no difference in the incidence of malignancies or hematological malignancies was demonstrated between placebo and eltrombopag treated patients. This is consistent with information derived from non-clinical research, where no malignant cell proliferation has been demonstrated upon co-incubation of eltrombopag with MDS cell lines, multiple leukemic cell lines and solid tumor cell lines (colon, prostate, ovary and lung).

